### 7.3.3 Major Adverse Cardiovascular Events (MACE)

Cardiac events of interest will be defined as the following preferred terms:

- Torsade de Pointes
- Ventricular tachycardia
- Ventricular fibrillation
- Ventricular flutter
- Syncope
- Seizures
- Sudden death
- Sudden cardiac death

A summary table of these 8 terms by PT only will be provided, with all terms included in the table even when the number of events is zero.

MACE will be summarized for the Primary, SoC1 / Combination and SoC2 / Monotherapy Populations. A supporting listing will be provided, with a flag for treatment emergent MACE.

### 7.3.4 Laboratory Data

Système International (SI) units provided by a central laboratory will be used for presenting all laboratory values.

Values below the lower limit of quantification (LLOQ) will be replaced by the value of the LLOQ.

The hematology and clinical chemistry parameters to be summarized are as follows:

- Hematology: Hematocrit, Hemoglobin, Leukocytes with differential count, Platelet (count)
- Clinical chemistry: Albumin, Alkaline phosphatase (ALP), Aspartate aminotransferase (AST), Alanine aminotransferase (ALT), Bilirubin (total), Calcium, Creatinine, Glucose, Potassium, Sodium

The values provided by the central laboratory in standard units as well as the flags for Low/Normal/High (L/N/H) values relative to the normal range or Normal/Abnormal classifications will be used for summaries.

	Plus-Project Statistical Analysis Plan	
	Protocol Number: GALACTIC-1	Version: 1

For the continuous parameters, the results and the change from baseline (for post baseline assessments) will be summarized by treatment and visit. This summary will be repeated in the SoC1 / Combination and SoC2 / Monotherapy Populations.

For any categorical parameters (including incidence of abnormalities), the results will be summarized by treatment and visit based on the number of subjects with non-missing data at the visit as the denominator.

Separate subject listings of abnormalities across all populations, sorted by SoC, will be presented showing all data within the abnormal parameter over the study for the respective subject.

All laboratory results will be listed, including all unscheduled visits.

Serum pregnancy results (at screening) and urinary pregnancy results (post-screening) will be listed per subject and visit.

### **7.3.5 Vital Signs (including Pulse Oximetry)**

Vital signs (including Pulse Oximetry) data from the ‘Vital Signs – Complete’, ‘Vital Signs – Brief’ and ‘Pulse Oximetry’ eCRFs will be used.

The vital sign parameters to be summarized are

- Diastolic and systolic blood pressure (mmHg),
- Heart rate (beats/min),
- Body temperature (°C),
- Respiratory rate (breaths/min),
- Hemoglobin saturation with oxygen (%),
- Body weight (kg),
- BMI (kg/m^2).

If body temperature is recorded in °F then the following formula will be applied:-

$$\text{Temperature (°C)} = 5/9 \times (\text{Temperature [°F]} - 32)$$

The results and the change from baseline (for post baseline assessments) will be summarized by treatment and visit for each parameter, repeated for all populations.

	Plus-Project Statistical Analysis Plan	
	Protocol Number: GALACTIC-1	Version: 1

### 7.3.6 ECG

ECG data from the ‘Electrocardiogram Local’ eCRF will be used.

The ECG parameters to be summarized are

- ECG Mean Heart Rate (beats/min),
- PR Interval (msec),
- QRS Duration (msec),
- QT Interval (msec),
- QTcF (Fridericia's Correction Formula) (msec).

The results and the change from baseline (for post baseline assessments) will be summarized by treatment and visit for each parameter.

The overall ECG interpretation (Normal/ Abnormal – Not Clinically Significant [NCS]/ Abnormal – Clinically Significant [CS]) will be summarized by visit based on the number of subjects with non-missing data at the visit as the denominator.

Each of the above summaries will be repeated for the SoC1 / Combination and SoC2 / Monotherapy Populations.

Separate subject listings of CS abnormalities across all populations, sorted by SoC, will be presented showing all data within the CS abnormal parameter over the study for the respective subject.

### 7.3.7 Physical Examination

Physical Exam data from the ‘Physical Exam’ eCRF will be used.

The results of the physical examination (Normal, Abnormal – NCS, Abnormal – CS) will be summarized by treatment and visit for each body system. These summaries will be repeated for all populations.

Separate subject listings of CS abnormalities across all populations, sorted by SoC, will be presented showing all data within the CS abnormal body system over the study for the respective subject.

### 7.3.8 Time to Premature Treatment Discontinuation

The date of premature treatment discontinuation will be derived from the ‘Disposition Study Completion’ eCRF.

	Plus-Project Statistical Analysis Plan	
	Protocol Number: GALACTIC-1	Version: 1

The time to premature treatment discontinuation (i.e. prior to Day 358, Week 52 – 1 week) in weeks will be derived as (date of treatment discontinuation – date of randomization +1)/7.

If a subject does not prematurely discontinue treatment prior to Day 358, they will be censored in the analysis at Day 359.

Summary tables of the time to premature treatment discontinuation by treatment group (as a continuous variable for those that prematurely discontinued), as well as Kaplan Meier plots by treatment will be produced. These summaries and plots will be repeated for all populations.

### 7.3.9 COVID-19

Cases of Covid-19 will be obtained from the ‘Covid-19’ eCRF form. Cases post first dose of study treatment will be summarized by treatment arm and split into the following periods:-

- Overall
- On treatment
- Post treatment

These summaries will be repeated for all populations.

## 9. CHANGES TO STATISTICAL ANALYSIS FROM PROTOCOL

The following clarifications have been made compared to the statistical analysis documented in the protocol at the time of writing (Version 7.0, 28 January 2022):

The protocol stated that two separate sensitivity analyses would be carried out for the primary estimand, and a tipping point analysis. The tipping point analysis described was looking for the tipping point between two sensitivity analyses, rather than relating to the primary analysis, and so was considered not to be informative and was removed. The second sensitivity analysis was also removed.

The protocol stated that for the endpoint of time to death, if fewer than 5% of subjects experienced the event during the study then only frequencies per treatment group would be displayed and no formal statistical analysis would be performed. The threshold for deaths has been removed and time to death will be analyzed regardless of the number of events.

In the logistic regression analyses the Wald test will be used rather than a likelihood ratio test.

The protocol defined a subgroup of subjects recruited prior to Protocol version 6.0 vs subjects recruited post v6.0, which is also removed.

[figure not shown]
## 10. AMENDMENT HISTORY OF SAP

Not Applicable.

	Plus-Project Statistical Analysis Plan	
	Protocol Number: GALACTIC-1	Version: 1

## 11. APPENDICES

### 11.1 Figure 3: Trial Design Schematic, Original Design

 Plus-Project Statistical Analysis Plan		
	Protocol Number: GALACTIC-1	Version: 1

## 11.2 Table 4: Schedule of Assessments

Visit	1	2	3	4	5	6	7	8	Withdrawal 	Follow up 
	Screening 	Baseline	Treatment							
		0	4	8	12	26	40	52	-	
Day			29	57	85	183	281	365		7 days after final study visit (+7 days)
Time window	6 weeks	0	±3	±3	±3	±7	±7	±7		
Informed consent	X									
HRCT sent to central review	X									
Demographics (including height, weight)	X									
Medical history	X									
Randomization		X								
In- /exclusion criteria	X	X								
Physical examination, vital signs	X	X	X	X	X	X	X	X	X	
HRQoL (SGRQ, SF-36)		X			X	X		X		
Dyspnoea index (UCSD-SOBQ)		X			X	X		X		
12-lead ECG	X	X	X	X	X	X		X	X	
Laboratory test (chemistry, haematology) 	X	X	X	X	X	X	X	X	X	
Urinalysis	X			X	X	X	X	X	X	
Pregnancy test 	X	X		X		X		X	X	
Biomarker sample		X	X		X	X		X		
Genetics sample 		X								
Spirometry (FVC, FEV1)	X	X	X	X	X	X	X	X	X	
SpO 2		X						X		
DLCO	X							X	X	

	Plus-Project Statistical Analysis Plan		
	Protocol Number: GALACTIC-1	Version: 1	

6MWT		X							XX	
Administer 1 st study medication (at clinic) and inhaler training 		X								
Dispense trial drug		X	X	X	X	X	X			
Compliance / drug accountability 			X	X	X	X	X	X	X	
Adverse events and conc. Meds 	X	X	X	X	X	X	X	X	X	X

**Notes:**

1. HRCT confirmation by central reading must be obtained as soon as possible following screening visit 1 and prior to visit 2
2. See Table 2 and Table 3 in Section 10.4.9 of the protocol.
3. In women of child bearing potential only: serum b-HCG will be required at visit 1 only, followed by urinary testing at subsequent visits.
4. This is optional and separate consent must be obtained. The sample can be taken at other study visits.
5. Subjects should be observed for 1 hour after the first dose to monitor for any acute adverse effects of study drug administration.
6. Includes checking the subject's use of the DPI device (Plastiape monodose inhaler).
7. The follow-up will be performed via a phone call.
8. Events occurring prior to randomization and administration of drug are considered as pre-treatment. Adverse events are also collected for up to the phone follow up.
9. FVC, DLCO and 6MWT will be performed as part of the withdrawal assessments.

	Plus-Project Statistical Analysis Plan	
	Protocol Number: GALACTIC-1	Version: 1

### 11.3 Primary Estimand Sensitivity and Tipping Point Analyses

A sensitivity analysis to test the robustness of the MAR assumption used in the main estimand analysis will be performed to assess the results with missing Week 52 FVC data.

Non-monotone missing data or missing data at other visits before week 52 will not be imputed. Multiple imputation will be used to handle missing data at week 52. The imputation model will be similar to the statistical model of the primary analysis.

For the imputation of week 52 data that is not available for reasons other than the occurrence of an ICE, the imputation model will be run on the subset of patients who prematurely discontinued trial drug but have been followed up for FVC measurements at week 52. FVC measurements that remain unobserved due to ICEs will still be handled as described in Section 7.2.1. Table 5 below contrasts the MAR approach used in the main estimand analysis with the MNAR approach used in the sensitivity analysis.

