### 7.2.1 Primary Efficacy Endpoint Analysis

The primary efficacy endpoint is the annual rate of decline in Forced Vital Capacity (FVC; expressed in mL over 52 weeks). Spirometry data provided by an external vendor showing the FVC (L) will be multiplied by 1000 to convert to mL. The analyses will be based on all FVC values obtained. Any FVC values post Day 453 will be omitted from the analyses.

The primary efficacy endpoint will be analyzed according to the estimand framework. Strategies for handling FVC data affected by the inter-current events (ICEs) of death, treatment discontinuation, and initiation of additional IPF therapy (pirfenidone or nintedanib) will be employed. Full details regarding use and imputation of FVC data in relation to ICEs are given in the next section.

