### 7.2.2 Main Estimand and Analysis

The primary analysis will test for superiority of GB0139 3mg compared to Placebo (Plc) for the annual rate of decline in FVC in mL over 52 weeks in subjects not receiving pirfenidone or nintedanib at baseline in the mITT Set. The main estimand for the primary efficacy endpoint is as follows:

- Population: Primary Population, mITT set.
- Variable of interest: Change from baseline in FVC in mL over 52 weeks
- Intercurrent events:
  - Death: FVC attributed the lowest value recorded in the trial when a patient dies

	Plus-Project Statistical Analysis Plan	
	Protocol Number: GALACTIC-1	Version: 1

- Treatment Discontinuation: Analysis will include any FVC measurements after randomised treatment discontinuation
- Initiation of additional IPF therapy (nintedanib or pirfenidone): Analysis will include any FVC measurements after initiation of additional IPF therapy
- Summary measure: Comparison of slopes assessed through the treatment by time interaction.

The null hypothesis is:

$H_0$ : There is no difference in the annual rate of decline in FVC in mL between GB0139 3mg and Plc

The alternative hypothesis is:

$H_a$  : There is a difference in the annual rate of decline in FVC in mL between GB0139 3mg and Plc

A restricted maximum likelihood (REML) approach will be used, with a random coefficient regression (random slopes and intercepts) model fitted to test the hypotheses. The decrease in FVC is assumed to be linear within each subject over 52 weeks [5].

Baseline FVC and time will be fitted as continuous covariates. The treatment group and the interaction term for time by treatment group will be added as fixed effects. Random subject intercept and time effects will be fitted and will be assumed to be normally distributed with arbitrary covariance matrix. The within-subject errors will be assumed to be independent and normally distributed with mean zero and a common variance. The Kenward-Roger approximation will be used to estimate denominators degrees of freedom.

The statistical model will be as follows:

$$Y_{itk} = (\alpha + a_i + \tau_k) + \beta_f FVCb_i + (\gamma + \beta_3 T_3 + g_i) t + \varepsilon_{it}$$

where:

$Y_{itk}$  is the change from baseline measured for ith patient at time t (actual time) in treatment group k

$t$  is the time since randomization in years

$T_3 = 1$  if the subject is in the GB0139 3mg group, otherwise  $T_3 = 0$

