$\beta_3$  is the effect of treatment on the slope compared to Placebo

$\alpha$  and  $\gamma$  are elements of the intercept and slope respectively

$a_i$  and  $g_i$  are random specific components of the intercept and slope respectively for the ith patient, assumed to be normally distributed with mean 0 and arbitrary covariance matrix

	Plus-Project Statistical Analysis Plan	
	Protocol Number: GALACTIC-1	Version: 1

$FVCb_i$  is the baseline FVC (mL) for the  $i$ th patient

$\tau_k$  is the intercept coefficient of the effect of treatment  $k$  ( $k=1, 2$ )

$\beta_f$  is the effect of 1ml increase in the baseline FVC

$\varepsilon_{it}$  is the random error for  $i$ th patient at time  $t$  assumed to be independent and normally distributed with mean 0 and variance  $\sigma^2$

This approach adopts a missing at random (MAR) assumption (i.e., the probability of an observation being missing depends only on observed measurements). Subjects with missing data at a particular time point still contribute to the analysis at that time point based on their other observed data used in the model (i.e., treatment, baseline FVC, and the FVC at baseline). Data that remain unobserved due to ICEs will be handled as described above. Other missing data will be imputed within the regression model under the MAR assumption.

The linearity assumption for the rate of change in FVC from baseline to week 52 will be explored graphically. Graphical displays will be provided of the mean ( $\pm$  SEM) observed FVC and mean change from baseline for each treatment group by visit.

The assumptions of the analysis will be checked by inspection of graphical displays of the residuals.

A cumulative distribution plot of the percentage of subjects by change from baseline in FVC in mL at week 52 will be presented.

The primary analysis detailed above will be repeated for the Primary Population, PP Analysis Set and for SoC1 / Combination and SoC2 / Monotherapy Populations (only for the mITT Analysis Set).

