**Table 5 – Missing Data Approaches**

Analysis	No FVC result but alive at Week 52	
	Handling of missing FVC result	Underlying assumption
Primary Estimand Analysis	Missing data handled by model.	Assumes missing at random. Discontinued subjects would have behaved similarly to subjects who did not discontinue who are in the same treatment group.
Sensitivity analysis	Based on the slope estimates for GB0139 dose and placebo among subjects who experience ICE without missing FVC data.	Subjects with a missing result would have behaved similarly to discontinued subjects with a result who are in the same treatment group.

The slope (SE) estimates of both treatment groups will be used in the sensitivity analysis. This approach is considered appropriate since the reasons for trial drug termination are expected to be similar between subjects with and without missing FVC data (discontinuation mainly due to AEs). The Sensitivity analysis corresponds to the assumption that in subjects with missing FVC data, the treatment effect would have persisted in the same manner as for subjects without missing FVC after trial drug discontinuation.

The number of imputations will be set to 1000 in order to ensure adequate efficiency for the estimation of missing data. For each imputed dataset, the same statistical model as defined for

	Plus-Project Statistical Analysis Plan	
	Protocol Number: GALACTIC-1	Version: 1

the primary analysis will be used for the analysis. See Section 7.2.1 for a description of the primary analysis model. The results will be pooled following the standard multiple imputation procedure. See Section 11.4 for further information on the implementation of the multiple imputation approach.

If the primary analysis and sensitivity analysis reach differing conclusions a tipping point analysis will be done. The tipping point analysis will be performed by applying an incremental shift from the imputed FVC value generated under MAR assumption toward the imputed FVC value generated under the MNAR assumption. The value of the shift that overturns the primary analysis result will represent the tipping point.

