##### Step 4: Impute any monotonic missing FVC data at 52 weeks using each slope

- a) Considering that the withdrawal of a subject leading to missing data can occur at any time during the study, the timepoint of the last available FVC value has to be taken into account to impute the missing FVC value at 52 weeks:
- b)  $FVC_{week\ 52\ imputed_{ij}} = \text{last FVC value available}_i + \hat{\beta}_{ij} * (\text{time between date of last FVC value available } i \text{ and planned 52 week timepoint [days]})$

	Plus-Project Statistical Analysis Plan	
	Protocol Number: GALACTIC-1	Version: 1

where  $i$  denotes the indicator of the  $i$ th subject,  $j$  the indicator of the  $j$ th imputation and  $\beta_{ij}^{\wedge}$  denotes a random slope sampled from the distribution mentioned above for the  $i$ -th subject in the  $j$ -th imputation.

- c) Create 1000 imputed FVC datasets for subjects with monotonic missing FVC data at 52 weeks including replicates of any FVC data collected in the study with the addition of the imputation specific 52 week result.
- d) Create 1000 identical FVC datasets for subjects with no monotonic missing FVC data at 52 weeks.
- e) Combine data from b and c.

Step 5: Run primary analysis model on each imputed dataset

Run the model of the primary analysis on each imputed dataset, using a "by \_IMPUTATION\_" statement to obtain 1000 parameter estimates (variable = estimate) and standard errors (variable = stderr).

Step 6: Combine the results obtained in step 4 using PROC MIANALYZE

```
Ods output ParameterEstimates=step5;
Proc Mianalyze data=step5 ;
modeffects estimate;
stderr stderr;
Run;
```

	Plus-Project Statistical Analysis Plan	
	Protocol Number: GALACTIC-1	Version: 1

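### SAP Sections 11.3 and 11.4 give conflicting rules on who is imputed in the missing-not-at-random check, and one rule leaves out subjects who stopped drug

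*SAP*

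**What the plan says.** - **ICEs.** SAP Section 7.2.1 announces strategies for the "inter-current events (ICEs) of death, treatment discontinuation, and initiation of additional IPF therapy", the last meaning nintedanib or pirfenidone.
- **Primary handling.** Section 7.2.2 gives a value to an unobserved FVC only for death (the lowest value recorded in the trial). For stopping drug it says "Treatment Discontinuation: Analysis will include any FVC measurements after randomised treatment discontinuation", with a matching line for added IPF therapy. For the rest, "Other missing data will be imputed within the regression model under the MAR assumption".
- **Sensitivity analysis, text.** Section 11.3 fits the imputation model in subjects who stopped drug early but still had Week 52 FVC. It introduces the target with "For the imputation of week 52 data that is not available for reasons other than the occurrence of an ICE" and adds that "FVC measurements that remain unobserved due to ICEs will still be handled as described in Section 7.2.1".
- **Sensitivity analysis, Table 5.** The table covers subjects who are alive at Week 52 without an FVC result. Its assumption is: "Subjects with a missing result would have behaved similarly to discontinued subjects with a result who are in the same treatment group".
- **Procedure.** Section 11.4 Step 4 is headed "Impute any monotonic missing FVC data at 52 weeks using each slope" and has no ICE exclusion. Step 1 takes the slopes from the primary model on observed data.
- **Triggers.** Section 7.2.2.4 runs the check only if the amount of missing data raises concern, with no threshold, whereas Section 11.3 says that it will be done. The tipping-point analysis in Section 11.3 runs only if the check and the primary analysis disagree.

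**The concern.** The subjects whose missing FVC is most likely to be informative are those who stop drug, or switch to licensed therapy, and then leave. The imputation model is fitted in discontinued subjects so that their slopes can stand in for this group. Under the literal Section 11.3 sentence the group is excluded, and the discontinued subjects' slopes go to subjects who had no ICE.

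Within the SAP, this is the only planned analysis of the primary endpoint that departs from MAR for living subjects. The MMRM in Section 7.2.2.4 and supplementary analysis 1 in Section 7.2.2.3 still rely on MAR, and supplementary analysis 2 changes only the value given at death. A check that imputes few of the relevant subjects is also less likely to disagree with the primary analysis, so it is less likely to trigger the tipping-point analysis. With two rules on the page, the choice could be made after results are known.

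**Working it through.** **1. The plan's own figure.** The only quantity nearby is the sample size: 141 at 2:1 (47 placebo, 94 active), difference 100 mL, SD 240 mL, two-sided 10%, power 75% (SAP 3.1).

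- SE = 240 × √(1/47 + 1/94) = 42.9 mL
- 100 / 42.9 = 2.33, and 2.33 − 1.645 = 0.69
- Φ(0.69) ≈ 0.754, which matches 75%

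The figure is reached with all 141 subjects contributing. No dropout allowance is built in, so no missing-data rate can be backed out of the sample size, and neither document states one.

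**2. Follow one subject through each rule.** Take a subject who stops drug at Week 20, has no later FVC and is alive at Week 52.

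| Source | Is this subject imputed? |
|---|---|
| 11.3 sentence with the 7.2.1 ICE list | No, if the value is missing because of stopping drug; sent back to primary handling |
| Primary handling (7.2.2) | No value assigned; falls to the MAR model |
| Table 5 | Yes: alive with no result |
| 11.4 Step 4 | Yes: monotone missing at Week 52 |

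A subject who starts nintedanib or pirfenidone and then has no FVC gets the same four answers.

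**3. Can the reason for missingness settle it?** Protocol Sections 10.5 (stopping treatment) and 10.6 (leaving the study) share several reasons: loss to follow-up, withdrawal by the subject and sponsor termination. One event can therefore be both the ICE and the reason that the visit is missing. The SAP has no rule for attributing it.

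**4. Which slopes are used?** Section 11.3 calls for a model in discontinued subjects with Week 52 FVC, and the Table 5 assumption agrees. Step 1 uses the primary model for each treatment group. Step 2 refers back to Section 11.3 for the distribution but does not correct Step 1. If Step 1 is followed, imputed slopes centre on the whole-arm slope, and the check stays close to MAR whoever is imputed.

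**5. Illustrative counts (assumptions, not document figures).** Let 10%, 20% or 30% of 141 be alive without Week 52 FVC, and let 80% to 100% of those have stopped drug. For the middle row: 0.20 × 141 = 28; 0.8 × 28 = 22; 28 − 22 = 6.

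| Alive, no Week 52 FVC | Left under MAR by literal 11.3 | Imputed by literal 11.3 | Imputed by Step 4 |
|---|---|---|---|
| 10%: 14 | 11–14 | 0–3 | 14 |
| 20%: 28 | 22–28 | 0–6 | 28 |
| 30%: 42 | 34–42 | 0–8 | 42 |

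These are counts of subjects. They say nothing about how far the slope difference would move.

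**The case against.** The best defence is that the sentence in Section 11.3 can be read harmlessly. Under treatment policy, stopping drug does not itself make FVC missing: the protocol lets such subjects stay and complete visits (Sections 6.2 and 10.5) and lists study withdrawal separately (Section 10.6). Someone who stops and later leaves is then missing because of withdrawal, which is not on the ICE list, and is imputed. Only death has a rule for unobserved values, so the return to primary handling would mean death alone. Table 5, Step 4 and the rationale under Table 5, which compares reasons for stopping drug in subjects with and without FVC, all fit this reading and probably show the intent.

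Much of this stands, and a programmer working from Step 4 would impute these subjects. It does not remove the conflict. Taking ICE to mean death alone fits poorly with Table 5, which draws its slopes from subjects who had an ICE and still have FVC. The withdrawal reading is nowhere stated and meets the overlap in reasons noted in step 3. Section 11.4 calls its steps guidance and refers back to Section 11.3 for the handling of missing data, so Step 4 does not clearly prevail.

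A reader might go further and infer that the plan imputes only subjects without an ICE, so that the check must agree with the primary analysis almost by construction. The documents do not support that. Table 5 and Step 4 say otherwise, and no calculation shows agreement.

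**Conclusion.** The conflict is real and should be resolved before unblinding. Two stated rules give different imputation sets, and one of them would largely defeat the missing-not-at-random check and the tipping-point analysis that follows from it. The primary estimate is unaffected, and the check is itself conditional under Section 7.2.2.4.

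The effect on the treatment comparison cannot be computed from the documents. The count of 11 to 42 subjects rests wholly on the assumed 10% to 30% and 80% to 100%. The finding itself needs only the ICE list in Section 7.2.1, the missing rule for unobserved values in Section 7.2.2, and the differing scopes in Sections 11.3 and 11.4.

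**What to change.** 1. In Section 11.3, replace the sentence that sets the imputation target with: *Impute Week 52 FVC for every subject alive at Week 52 with monotone missing FVC, whatever the reason, including after treatment discontinuation or start of additional IPF therapy; only deaths are handled by the composite value.* Remove or align the following sentence on values unobserved because of ICEs.
2. In Section 11.4 Step 4, add only the exclusion of deaths; its scope otherwise agrees already.
3. In Section 11.4 Step 1, take the imputation slopes and standard errors from discontinued subjects with Week 52 FVC, by treatment group, and use the number of those subjects when Step 3 converts the standard error to an SD.

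The cost is a few sentences in the SAP and a restricted model fit in the imputation program, with no new data. The number of such subjects in each arm is unknown. If it is small, the imputed slopes will be imprecise, and the SAP should say in advance how that will be reported.
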